11.4. Serious Adverse Experiences (SAE)	32
11.4.1. Serious adverse experience reporting	32
11.5. Medical Monitoring	33
12. Discontinuation and replacement of subjects	33
12.1. Early Discontinuation of the Study Treatment	33
12.2. Withdrawal of subjects from the study	33
12.3. Replacement of subjects	34
13. Protocol violations	34
14. Data Safety Monitoring	34
15. Statistical Methods and Considerations	35
15.1. General	35
15.2. Efficacy analysis	35
15.3. Safety analysis	35
15.4. Sample size and power	36
16. DATA COLLECTION, RETENTION AND CLINICAL MONITORING	36
16.1. Data collection instruments	36

16.2.	Data Management Procedures	36
16.3.	Security and Archiving of Data	37
16.4.	Availability and Retention of Investigational Records	37
16.5.	Monitoring	38
16.6.	Subject Confidentiality	38
17.	ADMINISTRATIVE, ETHICAL, REGULATORY CONSIDERATIONS	38
17.1.	Protocol amendments	38
17.2.	Institutional Review Boards and Independent Ethics Committees	38
17.3.	Informed Consent Form	39
18.	References	41

PROTOCOL SYNOPSIS

TITLE	IV Colistin for Pulmonary Exacerbations: Improving Safety and Efficacy
SPONSOR	[name] National Jewish Health [name]
FUNDING ORGANIZATION	Cystic Fibrosis Foundation Therapeutics, Inc.
NUMBER OF SITES	1
RATIONALE	When patients with cystic fibrosis (CF) develop acute pulmonary exacerbations (APE) secondary to Pseudomonas aeruginosa airway infection, their treatment regimens frequently include IV tobramycin or IV colistin. When we reviewed approximately 500 CF subjects receiving IV tobramycin or IV colistin when being treated for APE, patients receiving tobramycin had significantly more episodes of acute kidney injury. We propose to study conventional administration of tobramycin and colistin prospectively, in addition to a novel colistin dosing schedule which is based on serum levels of the drug, to assess how regimens compare for efficacy and safety.
STUDY DESIGN	This is a prospective randomized single center interventional trial enrolling adult CF subjects who are diagnosed with APEs by their treating physician and who, according to their treating physician, will receive either tobramycin or colistin for the treatment of Pseudomonas aeruginosa or other appropriate gram-negative rods, such as Achromobacter xylosoxidans . The study is designed to evaluate a) whether pharmacokinetically adjusted colistin dosing, given on a twice daily schedule (BID), provides a more favorable efficacy and safety profile versus standard colistin three times daily (TID) dosing, with no serum levels analyzed, and b) whether pharmacokinetic-adjusted twice daily colistin dosing compares favorably to standard once daily tobramycin dosing, based on efficacy and safety, during treatment of APE. The three treatment arms are as follows: standard colistin TID dosing (based on product insert and

	evidence based recommendations for CF ¹) b) pharmacokinetic-adjusted BID colistin dosing or c) standard tobramycin dosing once daily ² .
PRIMARY OBJECTIVE	
 1. To evaluate the efficacy (based on FEV₁ improvement) and safety (based on development of AKI) of standard colistin TID dosing ¹ versus PK-adjusted BID colistin dosing in adult CF subjects being treated for APE. 2. To evaluate the efficacy and safety of PK-adjusted BID colistin dosing versus standard tobramycin once daily dosing (8-10 mg/kg once daily²) in adult CF subjects being treated for APE.
SECONDARY OBJECTIVE	
 1. To evaluate for time to achievement of steady state with PK-adjusted colistin therapy. 2. To evaluate longitudinal differences in exacerbation rates and antimicrobial resistance between tobramycin and colistin use. 3. To evaluate differences in neurotoxicity and ototoxicity related side effects between study arms. 4. To evaluate the pharmacokinetics of colistin's active metabolites in a broad CF population. 5. To evaluate plasma pharmacokinetics of colistin's active metabolites with levels achieved in the sputum, in order to calculate epithelial lining fluid concentrations. 6. To evaluate for novel markers of nephrotoxic AKI, prior to serum creatinine increases, based on urine protein:creatinine ratios and the urine biomarker Nephrocheck® point-of-care assay.
NUMBER OF SUBJECTS	90
SUBJECT SELECTION CRITERIA: INCLUSION CRITERIA	CF patients 18 years or over who are diagnosed with APE based on CFF guidelines, and are chronically infected with P. aeruginosa , or other gram-negative bacteria, can produce sputum, undergo phlebotomy and provide written consent, will be eligible for participation, once their treating physician has determined that they should receive one of the two agents for APE treatment while hospitalized. Subjects able to receive either tobramycin or colistin as part of their IV antibiotic regimen will be randomized to one of three arms. If a treating physician deems that a subject cannot receive tobramycin due to vestibular or ototoxicity or bacterial resistance, the subject will be randomized to either standard or PK-adjusted colistin.

SUBJECT SELECTION CRITERIA: EXCLUSION CRITERIA	Presence of chronic renal insufficiency, with abnormal baseline creatinine >1.2.
TEST PRODUCT, DOSE, AND ROUTE OF ADMINISTRATION	Dosing of IV colistin will be determined based on serum concentrations of the drug on a BID dosing schedule.
CONTROL PRODUCT, DOSE AND ROUTE OF ADMINISTRATION	Dosing of IV tobramycin once daily will occur based on consensus guidelines and will be adjusted based on serum levels. Dosing of IV colistin TID will occur based on product insert (Perrigo Company).
STANDARD OF CARE TREATMENT	All study arms will be receiving APE treatment as a multi-drug therapeutic regimen, based upon CFF guidelines.
DURATION OF SUBJECT PARTICIPATION AND DURATION OF STUDY	Subjects will be on study for up to 14 days, or for the duration of their IV antibiotic treatment for APE while hospitalized. The study will enroll for 36 months.
CONCOMITANT MEDICATIONS	Allowed: Standard therapy for CF pulmonary exacerbations. Prohibited: none
PRIMARY ENDPOINT	
 1. Absolute change in FEV₁ % predicted with standard colistin TID dosing versus PK-adjusted colistin BID dosing, with APE treatment. 2. Absolute change in FEV₁ % predicted with standard tobramycin daily dosing versus PK-adjusted colistin BID dosing, with APE treatment. 3. Absolute change in FEV₁ % predicted with standard tobramycin daily dosing versus standard colistin TID dosing. 4. Safety of standard colistin TID dosing versus PK-adjusted colistin BID dosing in APE treatment, based on assessments of clinical symptoms, AKI occurrences during treatment (based on KDIGO criteria), change in urine protein:creatinine ratios, and an FDA approved renal injury biomarker test, Nephrocheck®, which measures: TIMP2 and IGFBP-7 (Astute Medical). 4. Safety of standard tobramycin daily dosing versus PK-adjusted colistin BID dosing and standard colistin TID dosing in APE treatment, based on assessments described in #3.

SECONDARY ENDPOINTS	
 1. Time to therapeutic dosing and number of therapy interruptions due to changes in creatinine with standard colistin, modified colistin, and standard tobramycin dosing. 2. Total number of IV doses delivered over the course of APE treatment. 3. Change in sputum microbiology profile following treatment with colistin versus tobramycin. 4. Number of exacerbations in the ensuing year and time to first pulmonary exacerbation following APE treatment. 5. Absolute change in Cystic Fibrosis Questionnaire-Revised (CFQ-R) respiratory domain score before and after APE treatment. 6. Number of episodes of neurotoxicity and ototoxicity in study arms, as noted on case-report forms. 7. Colistin peak, mid-point and trough during APE, for calculations of area under the curve (AUC).
PLANNED INTERIM ANALYSIS	When approximately 1/3 rd of patients have completed the study, an interim analysis for safety and outcome measures will be conducted. Serious adverse events will be monitored by the Medical Monitor on an ongoing basis throughout the study.
STATISTICS Primary analysis plan	
Statistical Methods: A detailed statistical analysis report will be written that will describe all analyses, tables, figures, and data listings generated for this study. All analyses will be performed using SAS ® (SAS Institute, Cary, NC, USA).
 
Analysis Populations: All analyses will be performed using an intent-to-treat (ITT) population, which is defined as all randomized subjects. Subjects who are discontinued from the study temporarily or permanently will remain in the analyses population according to ITT.
 
Demographic and Baseline Characteristics: Summary statistics will be calculated for demographic and baseline characteristics (age, sex, genotype, diabetic status, FEV₁ % predicted) time to therapeutic dosing for colistin versus tobramycin, number of therapy interruptions between study arms, and total number of IV antibiotic doses. Study medications and exposure to study drug data will be summarized in contingency tables.
 
Summary statistics and changes from

admission visit to end of treatment will be presented for FEV₁ % predicted and questionnaires, on an intent-to-treat basis, including all subjects receiving at least three days of colistin or tobramycin, and at least one efficacy assessment.

Analysis of Primary Endpoints:

Efficacy analysis: We will perform equivalence testing to show similarity of colistin treatments, as well as for colistin vs tobramycin treatments. For both comparisons, confidence intervals for difference in FEV₁ changes from pre to post treatment time points will be constructed, and equivalence tests to within 5% will be performed. Times to next pulmonary exacerbation and occurrence of neurotoxicity between standard colistin and PK-adjusted colistin will be analyzed using the Kaplan-Meier method. Subsequent pulmonary exacerbations in the ensuing year for all enrolled subjects, as well as antimicrobial resistance to tobramycin and colistin before and after treatment, will be summarized. Unless otherwise noted, 2-sided tests will be used with $\alpha = 0.05$.

Safety analysis: The safety profile of each colistin arm and the tobramycin arm will be assessed in terms of the following: incidence of AKI, incidence of treatment related clinical events (ototoxicity, vestibular toxicity, and neurotoxicity). Adverse event rates will be compared between treatment groups using logistic regression, adjusting for age, medications such as vancomycin, baseline FEV₁, admits in the previous year, exposure to nephrotoxic antibiotics in the previous 5 years, and diagnosis of CF related diabetes (CFRD) as covariates. Repeated measures within subjects will be accounted for by including a random intercept for subjects.

Summary statistics and changes from admission will be presented for serum Cr and urine:protein ratios. The urine protein:creatinine ratio will be assessed as a biomarker of drug toxicity. We will analyze Nephrocheck® assay results in a case control design. Subjects who develop AKI within each of the study arms will have urine thawed and analyzed by Nephrocheck® and those results will be compared to age, gender, and FEV₁, matched control urines obtained from subjects

	within the study who did not develop AKI. An adjusted odds ratio will be derived from a model fitted with unconditional logistic regression and adjusted for confounding variables. Estimates of odds ratios and 99% confidence intervals will be presented.
RATIONALE FOR NUMBER OF SUBJECTS	In a retrospective cohort 500 subjects, FEV1% improvement after tobramycin treatment during exacerbation therapy was 3% higher than in those receiving colistin; however, rates of acute kidney injury (rise in serum creatinine ≥ 0.3 mg/dL while on therapy) were 60% higher in tobramycin treated subjects versus standard colistin treated subjects. Since no preliminary data was available on less frequent colistin dosing, which theoretically would lead to less frequent episodes of kidney injury, we estimate we are powered to identify a safer method for dosing colistin with samples of 30 subjects per group, though we may be underpowered to find a significant FEV ₁ difference between groups.

Title: IV Colistin for Pulmonary Exacerbations: Improving Safety and Efficacy

1. Background

As the median projected survival of the CF population increases, a growing challenge for providers will be the strategic management of the comorbidities associated with chronic illness. An aging CF population chronically infected with *Pseudomonas aeruginosa* (PA) faces increased risk of diminishing *in vivo* clinical response to tobramycin, following years of aminoglycoside therapy for acute pulmonary exacerbations (APE). Results of CF antibiotic utilization surveys among accredited care centers have demonstrated the vital importance of tobramycin in pediatric APE treatment (98.5% of centers)³. Nearly ubiquitous use of tobramycin during childhood, together with the anticipated need for further antimicrobial treatment over 4 to 5 decades of life, necessitates the need to identify alternative strategies which are equally as potent, as tobramycin resistance and toxicities develop. Not surprisingly, CF sputum microbiology trends in the US have shown significant increases in aminoglycoside resistance (30.4% in 2008 versus 11.8% in 1995)⁴. While it is important to identify potent regimens against PA and other resistant gram-negative rods, the long-term use of nephrotoxic intravenous antibiotics increases the population's risk of renal disease⁵. Strategies to reduce toxicities from treatment, such as the establishment of optimal dosing intervals for tobramycin in the TOPIC trial⁶, have been an important advance in decreasing APE treatment toxicities.

Colistimethate sodium or colistin, a member of the polymyxin family of antibiotics, is a powerful treatment option for APE, particularly with multi-drug resistant PA. While it has excellent antimicrobial activity against PA⁵, there has classically been a reluctance to use the drug due to its reported nephro- and neurotoxicity. More recent studies in ICU and CF populations suggest that nephrotoxicity secondary to colistin is less common than previously thought and is reversible. Studies comparing nephrotoxicity of intravenous colistin and aminoglycosides in CF actually demonstrate reduced toxicity with colistin^{3,6}. A major limitation to its use, however, is the lack of human *in vivo* data regarding its pharmacokinetics (PK) and pharmacodynamics (PD)⁷. There is no widespread consensus on best dosing intervals to optimize pathogen eradication and reduce renal toxicity; partly because the drug never underwent PK modeling studies prior to its FDA approval in the 1950s. Today, though colistin is frequently substituted for tobramycin during exacerbations in patients who have developed resistance to tobramycin, it is unclear how to dose the regimen for both safety and maximal efficacy—*i.e.* once daily versus three times daily, similar to questions posed with tobramycin prior to the TOPIC trial.

Currently, acute kidney injury (AKI), formerly known as acute renal failure, in CF is far greater than the background rate in the general population. In pediatric CF patients, AKI occurs at 100 times the general rate of AKI in children, and is primarily related to nephrotoxic antibiotic use⁸. In adults with chronic *Pseudomonas* airway infection, indices of renal impairment have been detected in 31-42% of the population⁵. Thus, the challenge remains to devise antimicrobial treatment strategies which are powerful enough to minimize antimicrobial resistance but also avoid longitudinal harm.

One limitation to improving safety of antimicrobial drug monitoring has been the lack of availability of clinical assays to measure levels of colistin from the serum. Highly accurate analytical techniques, now available through the University of Colorado School of Pharmacy, now make pharmacokinetic (PK) and pharmacodynamic (PD) studies of colistin possible in order to establish optimal dosing regimens for colistin. This technology

will allow optimization of colistin dosing in order to maximize efficacy and reduce toxicity associated with this agent.

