3.2 Secondary Objectives

1. To evaluate for time to achievement of steady state with PK-adjusted colistin therapy.
2. To evaluate longitudinal differences in exacerbation rates and antimicrobial resistance between tobramycin and colistin use.
3. To evaluate differences in neurotoxicity and ototoxicity related side effects between study arms.
4. To evaluate the pharmacokinetics of colistin's active metabolites in a broad CF population.
5. To evaluate plasma pharmacokinetics of colistin's active metabolites with levels achieved in the sputum, in order to calculate epithelial lining fluid concentrations.
6. To evaluate for novel markers of nephrotoxic AKI, prior to serum creatinine increases, based on urine protein:creatinine ratios and the urine biomarker Nephrocheck® point-of-care assay.

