10 EVALUATIONS BY VISIT

10.1 Visit 1

1. Review the study with the subject (or subject's legal representative) and obtain written informed consent and HIPAA authorization.
2. Administer QoL questionnaire
3. Review respiratory culture results in the previous 12 months
4. Assign the subject a unique identification number.
5. Record demographics data.
6. Record medical history, including exacerbation criteria based on Rosenfeld score, baseline serum creatinine, and number of exacerbations in the preceding year.
7. Record concomitant medications.
8. Perform a complete physical examination.
9. Obtain and record vital signs.
10. Record oximetry.
11. Record results from blood and urine clinical laboratory tests (chemistry, hematology).

12. Record results from urine or blood pregnancy test (if female of child-bearing potential).
13. Record results from spirometry.
14. Record results from sputum culture microbiology.
15. Collect urine for Nephrocheck®

10.2 Visit 2

1. Administer QoL questionnaire
2. Record serum creatinine from daily clinical laboratory draws.
3. Collect urine for Nephrocheck®
4. Record urine protein from three times weekly clinical laboratory check.
5. Record tobramycin peak and trough from week 1 clinical laboratory draw
OR
Collect blood, sputum, and urine for colistin pk measurement.

10.3 Visit 3

1. Administer QoL questionnaire
2. Record serum creatinine from daily clinical laboratory draws.
3. Collect urine for Nephrocheck®
4. Record urine protein from three times weekly clinical laboratory check.
5. Record tobramycin peak and trough from week 2 clinical laboratory draw
OR
Collect blood, sputum, and urine for colistin pk measurement.

10.4 Visit 4

1. Administer QoL questionnaire.
2. Record concomitant medications.
3. Record spirometry.
4. Record serum creatinine from daily clinical laboratory draws.
5. Record results from sputum culture microbiology.
6. Record total number of IV antibiotics doses over the preceding 14 days.
7. Collect urine sample for Nephrocheck®.
8. Complete Case Report Form (for toxicities).

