[name] will monitor the data collection for accuracy and quality for the study. Data will be collected from subject medical and research records and maintained in electronic Case Report Forms (eCRFs) using REDCap (Research Electronic Data Capture), a secure web-based application that supports data capture for research studies.

15. Statistical Methods and Considerations

15.1 General: Summary statistics will be calculated for demographic and baseline characteristics (age, sex, genotype, diabetic status, FEV₁ % predicted) time to therapeutic dosing for PK-adjusted colistin versus tobramycin, number of therapy interruptions between study arms, and total number of IV antibiotic doses. Study medications and exposure to study drug data will be summarized in contingency tables. Summary statistics and changes from admission visit to end of treatment will be presented for FEV₁ % predicted and questionnaire results, on an intent-to-treat basis, including all subjects receiving at least three days of colistin or tobramycin, and at least one efficacy assessment. Subjects will be enrolled once.

15.2 Efficacy analysis: We will perform equivalence testing to show similarity of colistin treatments, as well as for colistin vs tobramycin treatments. For both comparisons, confidence intervals for difference in FEV₁ changes from pre to post treatment time points will be constructed, and equivalence tests to within 5% will be performed. These will be derived from linear mixed models fitted for FEV₁ that include a random intercept for subjects to account for repeated measures, and the following covariates: age, other medication, admits in the previous year, and diabetes. Nested random terms will be included in the model to account for repeated measures – one for subject and one for visit within subject. CFQ-R domain scores will be analyzed in a similar fashion. Times to next pulmonary exacerbation and occurrence of neurotoxicity between standard colistin and PK-adjusted colistin will be analyzed using the Kaplan-Meier method. Subsequent pulmonary exacerbations in the ensuing year for all enrolled subjects, as well as antimicrobial resistance to tobramycin and colistin before and after treatment, will be summarized. Unless otherwise noted, 2-sided tests will be used with $\alpha = 0.05$.

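### The tobramycin–colistin comparison of exacerbation rates has no between-arm model, and the preceding-year exacerbation count recorded at Visit 1 goes unused; adding both is a modest, nearly free improvement

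*Combined protocol and SAP*

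**What the plan says.** Secondary endpoint 4 (Synopsis and Section 5.2) is "Number of exacerbations in the ensuing year and time to first pulmonary exacerbation following APE treatment". It serves secondary objective 2 in Section 3.2: "To evaluate longitudinal differences in exacerbation rates and antimicrobial resistance between tobramycin and colistin use".

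Section 15.2, in words that the Synopsis repeats, gives these methods:

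- Time to first event: "Times to next pulmonary exacerbation and occurrence of neurotoxicity between standard colistin and PK-adjusted colistin will be analyzed using the Kaplan-Meier method". The tobramycin arm is not mentioned, and no covariate is attached.
- One-year count: "Subsequent pulmonary exacerbations in the ensuing year for all enrolled subjects" are to be summarised. No model, test or covariate is named.

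Section 10.1 (Visit 1, item 6) has the site "Record medical history, including exacerbation criteria based on Rosenfeld score, baseline serum creatinine, and number of exacerbations in the preceding year". Prior-year frequency is treated as prognostic elsewhere. The FEV1 mixed model in 15.2 adjusts for "age, other medication, admits in the previous year, and diabetes", and the adverse-event model in 15.3, which covers AKI, also includes previous-year admissions.

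Randomisation (Sections 4.1 and 8.1) is blocked on gender, FEV1 and enrolment time, not on exacerbation history. Under Section 6.2, subjects who cannot receive tobramycin are randomised between the two colistin arms only. Under Section 2.1, subjects who cannot receive colistin may enter only the tobramycin arm.

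**The concern.** The objective names a between-drug comparison of rates, and the plan gives no method for it. The one method named compares two of the three arms and discards every event after a subject's first. The covariate most directly related to the outcome is the same quantity measured a year earlier. It is already collected, and a close relative of it adjusts FEV1 and AKI.

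What is at stake is precision and interpretability on a secondary endpoint. With 30 per arm, a chance difference in prior exacerbation frequency can sit unadjusted in the result. For tobramycin versus colistin the arms also differ by design in who may enter them. Tobramycin and colistin are given open-label (Section 8.2) and interim analyses are planned (Synopsis, Section 14), so a model or covariate chosen after data have been seen would carry less weight than one written down now.

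**Working it through.** **Inputs from the documents.** 30 subjects per arm (15.4); two-sided 5% level (15.2); one year of exacerbation follow-up (9.1.8); mean rates of 1 exacerbation a year in the registry (Section 2) and 1.8 (tobramycin) and 2.3 (colistin) admissions a year in the retrospective cohort (1.1). Admissions are used as a proxy for exacerbations. The plan states no power, effect size or dispersion for this endpoint, so there is no figure to reproduce.

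**Assumed.** Subject rates follow a gamma distribution with relative variance k, shared by the prior and following year, and counts are Poisson given the rate. Treatment rate ratios of 0.5 and 0.7 are illustrative.

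**1. How much the covariate can explain.** With mean μ, the count variance is μ + kμ². The between-patient share, which is also the correlation between the two years, is r = kμ/(1 + kμ). The variance removed by adjustment is about r².

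| μ | k | r | r² |
|---|---|---|---|
| 1 | 0.3 | 0.3/1.3 = 0.23 | 0.05 |
| 1 | 0.6 | 0.6/1.6 = 0.375 | 0.14 |
| 2 | 0.3 | 0.6/1.6 = 0.375 | 0.14 |
| 2 | 0.6 | 1.2/2.2 = 0.55 | 0.30 |

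Simulated reductions in the variance of the log rate ratio over these settings, at rate ratios 0.5 to 1, are roughly 2–30%.

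**2. Power at rate ratio 0.5.** Simulation with 30 per arm and 1,000 trials per scenario (Monte Carlo standard error up to √(0.25/1000) = 1.6 points). The count model is Poisson with Pearson scale.

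| μ | k | First event, log-rank | Count, unadjusted | Count, adjusted |
|---|---|---|---|---|
| 1 | 0.3 | 41% | 50% | 52% |
| 1 | 0.6 | 33% | 45% | 48% |
| 2 | 0.3 | 52% | 75% | 81% |
| 2 | 0.6 | 39% | 65% | 75% |

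A separate run of 500 trials per scenario gave 31–47% for unadjusted Cox, 35–52% for adjusted Cox, 45–77% for the unadjusted count and 49–82% for the adjusted count. The covariate added about 2–6 points to the count model there. In the table it adds 2, 3, 6 and 10. Most of the gain therefore comes from using all events. Type I error of the count models stayed near 5% with or without the covariate.

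**3. Power at rate ratio 0.7.** Over the same settings power stays at or below about 35%. With μ = 1.8–2.3 and k = 0.2–1.0, it is 20–39% unadjusted and 30–41% adjusted.

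**4. Chance imbalance.** The SD of the between-arm difference in mean prior-year count is √(2(μ + kμ²)/30). At μ = 1.8, k = 0.2 this is √(2 × 2.448/30) = 0.40. At μ = 2.3, k = 1.0 it is √(2 × 7.59/30) = 0.71. The chance of a difference above 0.5 a year is then 22% and 48%. At μ = 1 the range is 8–17%.

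**5. Imbalance by design, tobramycin versus colistin.** Suppose a fraction f of a colistin arm is tobramycin-ineligible with 2.3 events a year, and everyone else has 1.8. With no drug effect, the colistin:tobramycin rate ratio is (1.8(1 − f) + 2.3f)/1.8:

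- f = 20%: 1.9/1.8 = 1.06
- f = 40%: 2.0/1.8 = 1.11
- f = 60%: 2.1/1.8 = 1.17

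The fractions are assumptions; the documents give none.

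**The case against.** The strongest reply is that this is an efficiency preference on a secondary endpoint that the plan treats descriptively. The count is only summarised, so no unadjusted test exists to lose power. Nothing in the documents suggests that a dosing schedule would halve exacerbations, and at rate ratio 0.7 the comparison is inconclusive under either analysis. The covariate does little for time to first event: one run of 800 trials per scenario gave log-rank against adjusted Cox of 41 v 40%, 37 v 38%, 49 v 51% and 38 v 45%. Negative binomial fits can also warn of non-convergence at this size, and the power figures above are for Poisson with Pearson scale. All of this stands. It limits the size of the gain but does not supply the missing method for objective 2.

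A reader might infer more than the documents support:

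- **That patients' usual exacerbation frequency dominates the comparison, or varies widely.** The documents give group and registry means, not between-patient spread. Under the assumed values the between-patient share (r in step 1) is 23–55%, and Poisson noise is the larger part in three of four settings.
- **That missing adjustment explains most of the lost power.** Discarding later events costs more.
- **That the unadjusted colistin comparison is biased.** Those two arms are randomised against each other; chance imbalance costs precision. The design-based concern applies to tobramycin contrasts only.

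The Synopsis promises a detailed statistical analysis report. It is not among the documents and cannot be credited with an adjustment.

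**Conclusion.** The point holds as an improvement, not as an error in the plan. Objective 2 lacks a between-arm method for exacerbation rates, the named first-event analysis omits tobramycin, and a relevant baseline value already collected is left out.

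Under the assumed dispersion of 0.3–0.6, mean of 1–2 a year and rate ratio of 0.5, the count model is the larger step and the preceding-year count a small further one. The covariate's benefit grows with dispersion, which the documents do not give. The trial would remain underpowered for a moderate effect on this endpoint. The covariate also does not repair the tobramycin contrast, which needs the eligibility restriction or stratification as well. The primary FEV1 and AKI conclusions are unaffected.

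**What to change.** In Section 15.2 and the matching Synopsis text:

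1. Compare the one-year exacerbation count between arms with a log-linear count model that allows overdispersion (Poisson with Pearson scale, or negative binomial). Include treatment arm, log(preceding-year count + 0.5), and log observed follow-up time as offset. If negative binomial is chosen, name a fallback for non-convergence.
2. Analyse time to first exacerbation with a Cox model containing the same covariate, and keep the Kaplan-Meier curves as the display.
3. Limit tobramycin–colistin contrasts to subjects eligible for all three arms, or stratify them by that eligibility. The comparison of the two colistin arms can use everyone randomised between them.

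The cost is mainly wording, plus one more model assumption than Kaplan-Meier. It is not quite free of data work. Scheduled visits end at Visit 4, and Section 9.1.8 documents exacerbations for a year without specifying a last-contact date, so each subject's follow-up time must be recorded. The start of the clock also needs one definition: the endpoint counts from treatment, Section 9.1.8 from enrolment. Eligibility for all three arms should be recorded at randomisation.
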